## **Clinical Investigation Plan**

### **1.0 SYNOPSIS**

Title:	A Post-Market Study Evaluating the Prodigy MRI TM and Proclaim Elite TM MR Conditional SCS Systems
Short Title:	SCS MRI PMCF
Purpose:	The purpose of this study is to confirm the safety of the Prodigy MRI and Proclaim Elite MR conditional SCS systems.
Objectives:	The primary objective of this study is to confirm the safety of the Prodigy MRI and Proclaim Elite MR conditional SCS systems.
	The secondary objective of this study is to confirm that the MRI scan does not affect the functionality of the Prodigy MRI or Proclaim Elite MR conditional SCS system.
Endpoints:	The primary endpoint is the rate of MRI scan-related adverse events.
	
 
The secondary endpoints are defined as:
 
Rate of successful MRI mode 'turn on/off' functionality
 
Rate of successful 'turn on/off' functionality for the stimulation
 
Rate of successful adjustments to the program
 
Rate of successful interrogations and uploads of the IPG parameters
 

Design:	The study will be performed as an international, multicenter, prospective, and single-arm design. The study will be conducted as a Post Market Clinical Follow Up (PMCF) study and the results will be submitted to the Notified Body: BSI Group (BSI).
	Enrollment: Subjects who have been implanted with a Prodigy MRI or Proclaim Elite SCS system and are either clinically indicated to receive an MRI scan, or will receive an MRI scan solely for the purposes of this study, will be approached to participate in this study prior to their MRI scan. If the subject matches all of the study eligibility criteria, they will be informed about the study to see if they are interested in participating. After the subject signs the informed consent, the enrollment is complete.
	Baseline: A baseline evaluation will be performed prior to the MRI scan.
	MRI scan: Once subject's eligibility for an MRI scan has been confirmed, the MRI scan will be performed according to the SJM IFU for the implanted MR conditional SCS system.
	Immediate follow-up post-scan: An immediate post-MRI scan follow-up assessment will be performed to determine safety and device functionality.
	1-month follow-up: Subject will return to the clinic 1 month after the MRI scan for a safety check and device functionality check.

SJM-CIP-10056 Study Name: SCS MRI PMCF

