# **Clinical Investigation Plan**

	The study is complete when data from 46 unique subjects who have undergone an MR scan has been collected
Devices used:	Prodigy MRI or Proclaim Elite MR conditional SCS systems may be used in this study. See section 5.0 for specific models.
Study Population	The subject population enrolled in this study will be comprised of male and female subjects. Subjects must meet the specific eligibility criteria to participate in the study. Approximately 49 subjects will be enrolled to collect data from 46 subjects. Each subject will be scanned only one time for the purposes of this study.
Inclusion/Exclusion Criteria	
 
Inclusion Criteria
 
Patient has been implanted with a Prodigy MRI or Proclaim Elite MR conditional SCS system
 
Patient will receive an MRI scan in compliance with the IFU for the implanted MR conditional SCS system
 
Patient is ≥ 18 years of age
 
Patient must be willing and able to comply with study requirements
 
Patient must indicate his/her understanding of the study and willingness to participate by signing an appropriate Informed Consent Form
 
Exclusion Criteria
 
Patient has another implanted device (active or passive) that prohibits safe scanning
 
Patient has previously experienced an MRI scan-related adverse event
 
Patient is currently enrolled in another Abbott study that collects MRI safety data
 
Patient is incapacitated, is unable to read or write, or is pregnant or breastfeeding
 

Data Collection	
 
Data will be collected at Enrollment, Baseline, pre-MRI scan, MRI scan, post-MRI scan, and 1-Month follow-up.
 
Inclusion/Exclusion Criteria
 
Demographics
 
Medical Condition indicated for an MRI scan
 
Implanted SCS system information
 
Subject eligibility for MRI scan
 
MRI scan parameters
 
Device functionality
 
Safety events
 

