The devices used in this study have received CE mark and are being implanted in subjects. CE mark was granted based on preclinical device testing. This study will be conducted as a post-market clinical follow up (PMCF) study to collect additional scientific data to support the CE label for Prodigy MRITM and Proclaim EliteTM systems. Patients with an existing Prodigy MRI or Proclaim Elite MR conditional system who either undergo an MRI scan as standard of care, or agree to an MRI scan for study purposes, will be interviewed before the scan, after the scan, and 30 days later to determine device functioning and record any related adverse events. The rate of MRI scan-related adverse events will be used to evaluate the safety of these MR conditional SCS systems when used in compliance with the approved requirements.

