### 4.6.2 Secondary endpoint

The secondary endpoints are defined as:

- Rate of successful MRI mode 'turn on/off' functionality
- Rate of successful 'turn on/off' functionality for the stimulation
- Rate of successful adjustments to the program
- Rate of successful interrogations and uploads of the IPG parameters

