## **Clinical Investigation Plan**

Visit Study Activity	Enrollment (in clinic, prior to MRI scan)	Baseline (in clinic, prior to MRI scan)	MRI scan (in clinic, pre-, during, and post-scan	1 Month follow up (in clinic, 1 months ± 10 days since MRI scan)	Unscheduled	Additional surgery
Inclusion/Exclusion Criteria Check	Х					
Demographics Collection		Х				
Collection of Medical Condition indicated for MRI scan		Х				
Subject eligibility for MRI scan Check			X (pre- scan)			
Lead and IPG data Collection		Х				Х
Programming Functionality			X (pre- and post-scan)	Х	Х	
Device Functionality Check			X (pre-and post-scan)			
MRI Scan			X			
MRI Scan Parameters Collection			Х			
Determine Reason for the Visit and Action Taken					Х	Х
Adverse Events Check		(X)	(X)	(X)	(X)	(X)
Protocol Deviation	(X)	(X)	(X)	(X)	(X)	(X)

(X) if applicable

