### **Programming Functionality:**

## **Clinical Investigation Plan**

Information regarding the ability to re-program will be collected at pre- and post-scan, during the 1-month follow up visit and at unscheduled visits.

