### **Device Functionality:**

Data regarding the device functionality, including impedance check, will be collected pre-and postscan.

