### 6.5.1 Pre-scan

- Subject eligibility for MRI scan
- Device functionality, including impedance check
- Programming functionality
- AE and/or protocol deviation (if applicable)

MRI scan will be performed. Ensure to follow the instructions as mentioned in the MRI Procedure manual.

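### Synopsis and schedule differ on a 1-month device functionality check, and Section 12.1 gives the functionality endpoints neither a visit nor a pre-scan reference

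*Combined protocol and SAP*

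**What the plan says.** **Timing.** The synopsis (Section 1.0, Design) says of the 1-month visit: "Subject will return to the clinic 1 month after the MRI scan for a safety check and device functionality check". The background (Section 2.0) says patients "will be interviewed before the scan, after the scan, and 30 days later to determine device functioning and record any related adverse events".

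The operative sections read differently. Section 6.2 states: "Data regarding the device functionality, including impedance check, will be collected pre-and postscan". Table 2 marks the row "Device Functionality Check" at the MRI scan visit only, before and after the scan, and its 1-month cell is empty. Section 6.5.1 lists "Device functionality, including impedance check" before the scan, and Section 6.5.2 lists device functionality after it. Section 6.6 lists two items at 1 month: programming functionality, and adverse events or deviations. Section 6.2 describes programming functionality as a separate item: "Information regarding the ability to re-program will be collected at pre- and post-scan, during the 1-month follow up visit", and also at unscheduled visits.

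**Endpoints and analysis.** The secondary objective (Section 4.5.2) is to confirm that the scan leaves the system's functionality unaffected. Section 4.6.2 names four success rates. The first is "Rate of successful MRI mode 'turn on/off' functionality"; the others are stimulation on/off, program adjustments, and interrogation with upload of the generator's parameters. None carries a visit. Section 12.1 plans, for each, a count, a percentage and a Clopper-Pearson 95% interval.

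**The concern.** There are two separate issues.

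First, sites work from Table 2 and Section 6.6. If the synopsis means the full device functionality check at 1 month, sites following the schedule will not do it, and the scheduled 1-month functionality data will cover re-programming only. If the synopsis means something narrower, it suggests more 1-month evidence than the study is set up to collect.

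Second, and more important, whether a scan affects function is a before-and-after question. A single success percentage does not answer it. With no visit named, it is open whether the figure is pre-scan, immediate post-scan, 1-month or pooled. With no pre-scan reference, a fault already present when the subject arrived counts the same as a function lost after the scan.

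**Working it through.** **Step 1: the schedule, side by side.**

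| Source | Device functionality | Programming functionality |
|---|---|---|
| Synopsis, Design | 1-month check stated | not named |
| Section 2.0 | device functioning, by interview, at 30 days | not named |
| Table 2 | pre-scan, post-scan | pre-scan, post-scan, 1 month, unscheduled |
| Section 6.2 | pre-scan, post-scan | pre-scan, post-scan, 1 month, unscheduled |
| Sections 6.5.1 and 6.5.2 | pre-scan, post-scan | pre-scan, post-scan |
| Section 6.6 | not listed | 1 month |

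Leaving aside unscheduled visits, Table 2 gives the Device Functionality Check 2 time points and programming functionality 3. The operative sections agree with one another; the synopsis, and more loosely the background, do not agree with them.

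**Step 2: endpoints against the 1-month items.** Program adjustment matches the ability to re-program. For MRI mode on/off, stimulation on/off and interrogation/upload, no section says which check supplies the result, and Appendix H keeps the case report forms under separate cover. So 1 of 4 clearly has a scheduled 1-month item and 3 of 4 are undetermined. Impedance is not a secondary endpoint.

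**Step 3: what one percentage can show.** The plan states no target or power for these endpoints, so there is no figure to reproduce. The denominator of 46 scanned subjects comes from Section 12.2. It does reproduce for the primary endpoint: in an exact one-sided 5% test of 10% against 1%, 46 subjects with at most 1 event give an actual alpha of 0.0480 and power of 0.922.

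Take a function tested before and after the scan in 46 subjects, and assume 0 to 3 post-scan failures. These counts are illustrative; the documents give no fault frequency. For x successes in n, the Clopper-Pearson limits are:

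- lower = Beta quantile(0.025; x, n − x + 1)
- upper = Beta quantile(0.975; x + 1, n − x)
- when x = n, lower = 0.025^(1/n) and upper = 1

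| Post-scan failures | Post-scan success, all scanned (95% interval) | Among pre-scan passers, if every fault pre-dated the scan | Among pre-scan passers, if every fault followed the scan |
|---|---|---|---|
| 0 | 46/46 = 100% (92.3% to 100%) | 46/46 | 46/46 |
| 1 | 45/46 = 97.8% (88.5% to 99.9%) | 45/45 = 100% (lower limit 92.1%) | 45/46 = 97.8% |
| 2 | 44/46 = 95.7% (85.2% to 99.5%) | 44/44 = 100% (lower limit 92.0%) | 44/46 = 95.7% |
| 3 | 43/46 = 93.5% (82.1% to 98.6%) | 43/43 = 100% (lower limit 91.8%) | 43/46 = 93.5% |

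The second column is the same under both histories. The third and fourth lead to opposite conclusions on the secondary objective, and a summary of the form in Section 12.1 cannot tell them apart.

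**The case against.** The best reply on timing is that the conflict is one of terminology. The synopsis data list has a single item, "Device functionality", and no programming item. Section 8.3 applies the same term to the Section 4.6.2 endpoints, which include program adjustment. On that usage the 1-month programming check is the check the synopsis has in mind. Section 2.0 is weak support for the contrary reading, because it speaks of an interview. This softens the conflict but does not remove it: Table 2 and Sections 6.2, 6.5.1 and 6.5.2 list device and programming functionality as separate items.

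A reader might go further and infer that three of the four secondary endpoints will have no 1-month data. The documents do not support that. They do not map endpoints to checks, and the case report forms may record these functions under programming. Unscheduled visits (Section 6.7) and additional surgery (Section 6.8) would also pick up some late faults.

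On the analysis, it is fair to say that the secondary endpoints are descriptive, that Section 12.3 sets no pass/fail criteria, and that nothing in Section 12.1 forbids reporting by visit. It is also fair that eligibility for the scan is checked beforehand and the scan must follow the device instructions, so subjects with faulty devices may seldom be scanned; the protocol text does not say whether a functional fault bars a scan. These points limit how large the problem may be. They do not supply the missing visit or pre-scan reference, and a descriptive summary still has to describe the quantity the objective asks about.

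**Conclusion.** The point holds in two parts of unequal weight. The synopsis, and loosely the background, disagree with Table 2 and Sections 6.2 and 6.6 about 1-month device functionality and must be reconciled; whether any 1-month endpoint data would actually be missing cannot be determined from the protocol. The stronger part is Section 12.1: as written, it cannot separate a pre-existing fault from a loss of function after the scan, which is the secondary objective.

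The size in practice is unknown. The illustration assumes 46 subjects tested before and after the scan with 0 to 3 failures; it shows what the summary cannot distinguish, not how often that will matter. It also assumes that each function is recorded pre-scan, which the protocol states for device and programming functionality in general but not endpoint by endpoint. The primary endpoint and the sample size are unaffected.

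**What to change.** 1. **Reconcile the timing.** Either mark the Device Functionality Check at the existing 1-month clinic visit in Table 2 and Sections 6.2 and 6.6, or reword the synopsis and Section 2.0 and limit the 1-month functionality conclusion to re-programming. The first option costs a short check, a block on the case report form, and a programmer at that visit (Section 5.4 requires one only at the scan). The second costs wording only.
2. **Map the endpoints.** State in Section 4.6.2 or 12.1 which check, at which visit, supplies each of the four endpoints.
3. **Complete Section 12.1.** Keep the overall success rate with its exact 95% interval, and report each endpoint by visit: pre-scan, immediate post-scan, and 1 month where collected. For functions recorded both before and after the scan, add a pre-to-post table and the success rate among devices that passed pre-scan. Do not apply that restriction to MRI mode on/off, where a pre-scan failure is itself a failure of the endpoint.

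Item 3 costs wording and one table, with no new data where the forms already record the function at both times. Where they do not, the forms need a matching pre-scan field.

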# **Clinical Investigation Plan**

	The study is complete when data from 46 unique subjects who have undergone an MR scan has been collected
Devices used:	Prodigy MRI or Proclaim Elite MR conditional SCS systems may be used in this study. See section 5.0 for specific models.
Study Population	The subject population enrolled in this study will be comprised of male and female subjects. Subjects must meet the specific eligibility criteria to participate in the study. Approximately 49 subjects will be enrolled to collect data from 46 subjects. Each subject will be scanned only one time for the purposes of this study.
Inclusion/Exclusion Criteria	
 
Inclusion Criteria
 
Patient has been implanted with a Prodigy MRI or Proclaim Elite MR conditional SCS system
 
Patient will receive an MRI scan in compliance with the IFU for the implanted MR conditional SCS system
 
Patient is ≥ 18 years of age
 
Patient must be willing and able to comply with study requirements
 
Patient must indicate his/her understanding of the study and willingness to participate by signing an appropriate Informed Consent Form
 
Exclusion Criteria
 
Patient has another implanted device (active or passive) that prohibits safe scanning
 
Patient has previously experienced an MRI scan-related adverse event
 
Patient is currently enrolled in another Abbott study that collects MRI safety data
 
Patient is incapacitated, is unable to read or write, or is pregnant or breastfeeding
 

Data Collection	
 
Data will be collected at Enrollment, Baseline, pre-MRI scan, MRI scan, post-MRI scan, and 1-Month follow-up.
 
Inclusion/Exclusion Criteria
 
Demographics
 
Medical Condition indicated for an MRI scan
 
Implanted SCS system information
 
Subject eligibility for MRI scan
 
MRI scan parameters
 
Device functionality
 
Safety events
 

## **Clinical Investigation Plan**

### 2.0 BACKGROUND AND JUSTIFICATION FOR CLINICAL STUDY

Spinal cord stimulation (SCS) involves the application of electrical stimulation to the large myelinated fibers of the dorsal column via electrical leads placed in the epidural space. SCS is minimally invasive, reversible and has been used successfully to help manage a variety of pain conditions including diabetic neuropathy, failed back surgery syndrome, complex regional pain syndrome, phantom limb pain, ischemic limb pain, as well as postherpetic neuralgia and acute herpes zoster pain.

A systematic review and meta-analysis of SCS in refractory neuropathic back and leg pain documented that SCS reduces pain, improves quality of life, reduces analgesic use, allows some patients to return to work, and may also result in significant cost savings over time with minimal significant adverse events. Because chronic pain patients continue to live normal lives using SCS, they may develop unrelated medical conditions that require medical imaging, such as an MRI, as part of their standard care. An examination of the Truven Health MarketScan Research Database estimates that 82% - 84% of patients eligible for SCS will require an MRI at some point within 5 years of implant.

MRI is a diagnostic method for viewing high quality two and three-dimensional images of the body. MRI systems generate three electromagnetic fields (i.e. a static magnetic field, a time-varying gradient magnetic field, and a radiofrequency field) that are used to produce the image. All three of these fields interact with implanted devices, creating hazards for the device, the subject, or both. Due to these risks, currently marketed implantable generators (IPGs), leads, or accessories may be contraindicated for use in an MRI environment.

Abbott (formerly St. Jude Medical) has developed MR conditional neurostimulation systems designed to mitigate such interactions. These systems provide the option for conditionally safe scanning of subjects when the scan is performed according to approved guidelines. MRI compatible devices improve patient care by reducing limitations that would otherwise prevent patients from taking advantage of this commonly used diagnostic tool.

The devices used in this study have received CE mark and are being implanted in subjects. CE mark was granted based on preclinical device testing. This study will be conducted as a post-market clinical follow up (PMCF) study to collect additional scientific data to support the CE label for Prodigy MRITM and Proclaim EliteTM systems. Patients with an existing Prodigy MRI or Proclaim Elite MR conditional system who either undergo an MRI scan as standard of care, or agree to an MRI scan for study purposes, will be interviewed before the scan, after the scan, and 30 days later to determine device functioning and record any related adverse events. The rate of MRI scan-related adverse events will be used to evaluate the safety of these MR conditional SCS systems when used in compliance with the approved requirements.

### 3.0 RISKS AND BENEFITS OF THE CLINICAL STUDY

### 3.1 Description of subject population

The subject population enrolled in this study will be comprised of male and female subjects who have a previously implanted Prodigy MRI or Proclaim Elite MR conditional SCS system. Subjects must meet the specific eligibility criteria and provide informed consent to participate in the study.

### 3.2 Anticipated clinical benefits

The primary benefit of the MR conditional SCS systems is that they provide subjects with the option to receive a MRI scan when clinically necessary, while defining the conditions for use that maximize subject safety.

If subjects agree to take part in this study, there may or may not be direct medical benefits to individual subjects. The scientific use of the data collected in this study is to support the CE label of the Prodigy MRI and Proclaim Elite MR conditional SCS systems by confirming they are conditionally safe for MRI scans.

### 3.3 Potential Adverse Effects

The Prodigy MRI and Proclaim Elite MR conditional SCS systems have been designed to minimize the potential adverse effects that may cause subject harm. The following potential adverse effects may occur in the MRI environment:

- Lead electrode heating resulting in tissue damage or serious subject injury
- IPG heating resulting in tissue damage in the implant pocket or subject discomfort or both
- Induced currents on leads resulting in overstimulation or shocking sensations
- Damage to the IPG or leads causing the system to fail to deliver stimulation or causing the system to deliver overstimulation
- Damage to the functionality or mechanical integrity of the IPG resulting in the inability to communicate with the IPG
- Movement or vibration of the IPG or leads

### 3.4 Residual risks associated with the study device, as identified in the risk analysis report.

The clinical risks associated with neurostimulation systems for SCS applications are well known. Many of the clinical risks may develop as a consequence of not following the manufacturer recommended guidelines at the time of performing the MRI scans.

Any potential residual risks are considered to be outweighed by the benefits, and the overall residual risk was determined to be acceptable. Clinical evidence demonstrates acceptable safety and performance of the study device.

### 3.5 Risks associated with participation in the clinical study

The risks involved with this study are comparable to those associated with the implant of any other commercially available MR conditional SCS system.

### 3.6 Risk-to-benefit rationale

Since no design changes exist between the Prodigy MRI and Proclaim Elite MR conditional SCS systems and the predicate SCS systems, except for implementation of the MRI Mode, the non-MR performance of these products is already well established.

In addition, the clinical evidence demonstrates that the safety and performance of the study device, when used under the conditions and for the purposes intended, as specified by the manufacturer, are in compliance with the Requirements of the AIMD Directive 90/385/EEC, including the Essential Requirements.

